4.4 Randomization

After informed consent, subjects will be randomly assigned to either amantadine or placebo. For intention-to-treat analysis, subjects will be considered to be randomized as soon as an assignment is made. For per-protocol analyses, subjects will be considered to be randomized after receiving the first dose of study medication. The Investigational Drug Service (IDS) at the University of Pittsburgh will prepare and

dispense study drug and maintain the block randomization list. At randomization, subjects will be stratified by PCAC strata and presence of early malignant patterns on EEG recording (these EEG patterns must have stopped by time of randomization, because continued malignant EEG is an exclusion). Both of these have been associated with outcome. [2, 16, 32, 3.C.1.b]

Table 2. Inclusion and Exclusion Criteria

Inclusion Criteria	Exclusion Criteria
Non-traumatic cardiac arrest	Written do not attempt resuscitation (DNAR) reported to providers before randomization
Age 18 years or more	Known prisoner or pregnancy
Defibrillation and/or chest compressions by healthcare providers	Lack of motor response to pain and absent N2O response on SSEP prior to randomization.
Return of spontaneous circulation	Initial CT demonstrating brain edema (defined as grey white ratio <1.2)
	Presence of malignant pattern on EEG at time of randomization.
	Next of kin unwilling to provide supportive care for at least one week after enrollment.
	Creatinine clearance <50mL/min
	Presently using other dopaminergic agent

4.5 Intervention

Subjects assigned to the intervention arm will receive a dose of 100mg of amantadine, administered twice daily (at 6 am and 12 noon) for up to 7 days. The timing selected reflects the standard times used in our neurologic intensive care unit for this medication. **Subjects assigned to the placebo arm** will receive a dose of placebo that will appear identical to the amantadine. The amantadine and placebo will be made by the University of Pittsburgh IDS.

4.6 Allocation Concealment

Amantadine and placebo will appear identical. Drugs will be only have numerical identifiers when handled by the treating nurse and team. Unblinding can be provided to the treating team by the IDS only after consultation with the principle investigator or in predefined emergency situations. These

situations include severe allergic reactions not attributable to any other drug or unexplained tachydysrhythmia requiring cardioversion.

4.7 Justification for Timing of Intervention

One side effect of temperature management is a decrease in gastrointestinal motility. This returns to normal in the majority of patients after rewarming is completed. This will occur by 72 hours. As amantadine is only available in an oral form, decreased gastrointestinal motility could affect absorption. As noted in the preliminary data above, development and persistence of malignant EEG patterns is associated with poor neurologic outcome independent of initial illness severity. [Section 3.C.1.b] This design will allow these patients to be diagnosed with persistent malignant EEG patterns and excluded from the study.

4.8 Pharmacokinetic Measurements

Plasma concentrations of amantadine will be determined using solid phase extraction and a validated ultra-high performance liquid chromatography tandem mass spectrometry adapted from Arndt et al. [33] A 5 ml sample of blood will be obtained in citrated tubes, centrifuged (1000g x 15 minutes), decanted, and plasma frozen at -80°C until assay. Sampling will occur at 8 time points; daily “peak” levels 1-2 h following the afternoon dose on days 1-4 and “trough” levels immediately prior to 6 AM dose on days 2-5. This sampling strategy is designed to both confirm enteral absorption and to permit post-hoc analyses of any differential effect of amantadine based on plasma levels achieved in the study. The 4 days of sampling will capture steady-state levels (amantadine half-life is ~17 h) and also spans the period of greatest vulnerability for hypothermia-induced changes in drug pharmacokinetics if they should occur.

4.9 Monitoring of Compliance:

[name] leads a unique Post-Cardiac Arrest Service that has cared for this population since 2007. This ensures standardization of prognostic workup and clinical care outside of the care delineated in this study protocol. At enrollment, a trained research assistant will prospectively record pertinent information on the subject. The research assistant will also facilitate obtaining study drug from IDS to ensure drug administration in a timely fashion. The PI will perform random data spot checks, audits and will oversee the database and maintain quality.

4.10 Ancillary Care

It is critical to control for potential effect modifiers that occur when a patient is hospitalized after resuscitation from cardiac arrest.

Table 3. EEG and seizure definitions. MSE- myoclonic status epilepticus, GPEDs- generalized periodic epileptiform discharges, NCSE- nonconvulsive status epilepticus, EDs- epileptiform discharges.

Interpretation	Definition
Electrographic seizure	Repetitive generalized or focal spikes, sharp waves, spike-and-wave or sharp-slow wave complexes at ≥ 3 Hz or sequential rhythmic, periodic or quasi-periodic waves at ≥ 1 Hz with unequivocal evolution in frequency, morphology, or location lasting at least 10 seconds.
NCSE	Impaired consciousness with: 
1. A continuous single electrographic seizure lasting 30 minutes or greater or recurrent electrographic seizures lasting for over 30 minutes.2. Presence of GPEDs lasting at least 30 minutes at a rate ≥ 2.5 Hz.3. Presence of GPEDs lasting at least 30 minutes at a rate of ≥ 1 Hz with unequivocal evolution in frequency, morphology, or location over time.
MSE	More than 30-minute period of myoclonic jerks or subtle facial movements locked in with bursts in a burst-suppression pattern or associated with GPEDs.
Interictal GPEDs	GPEDs at a rate of < 2.5 Hz not satisfying criteria 3
EDs	Spikes, polyspikes, sharp waves, spike-and wave or sharp-slow waves occurring independently, periodically (GPEDs) or during burst-suppression.

[figure not shown]
Experts have recommended a standardized approach that includes targeted temperature management to optimize outcomes following cardiac arrest. [4, 8, 17] Our prior work has demonstrated that initial critical care management of the post-cardiac arrest patient has a large influence on neurological recovery and survival. [5, 26] Case control studies have reported improved outcomes in patients receiving combinations of hospital-based treatments compared to historical controls. [5, 24] We have shown that early use of coronary angiography and primary PCI is associated with good neurologic prognosis. [6, 8, 34] Our work through the ROC cardiac arrest registry has demonstrated that patients who were treated to a receiving hospital that had a coronary catheterization laboratory had better outcomes compared to those who were not. [8] Collectively, these studies demonstrate that hospital-based care of those resuscitated from cardiac arrest impacts patient outcomes and may modify the effect of interventions for cardiac arrest. We have addressed this issue for all subjects will be cared for by the Post Cardiac Arrest Service at UPMC-Presbyterian and receive standardized post arrest care delivered by the Post Cardiac Arrest Service.

4.11 EEG Protocol

We obtain a 22-channel digital EEG with simultaneous video recording on all patients resuscitated from cardiac arrest in our facility. This permits correlation of motor activity with electrographic findings and allows for accurate diagnosis of malignant EEG patterns. Contemporaneous interpretation is provided by the Department of Neurology. Subjects will be classified as demonstrating a malignant pattern or not using standard definitions. **[Table 3]** Locally, the PCAC II illness severity phenotype with malignant EEG patterns has a markedly reduced survival when compared to PCAC II illness severity without malignant EEG patterns.

Thus, subjects will be stratified on PCAC and (in the PCAC II illness severity subjects) presence of malignant EEG pattern prior to randomization. If malignant patterns do develop, we will provide therapy to suppress the EEG and any clinical evidence of seizures. **[Figure 3]** This ensures a standard approach to all subjects in the study. Importantly, subjects with malignant EEG patterns that persist beyond 48 hours are excluded from the study and will not be enrolled.

Figure 3. Standardized antiepileptic treatment algorithm for malignant EEG patterns. (Malignant= GPED's, MSE, NCSE)

4.12 Justification for Outcome Measures

We have chosen the rate of awakening as the primary outcome in this study. This short-term outcome is appropriate to determine if a potential for benefit exists. [35] Awakening is a prerequisite for a good neurologic outcome. [17] Persistent coma is the most common reason for withdrawal of care (56%) while multiple organ failure is the etiology of death in a minority (17%) of patients. [2]. Prior literature is hindered by withdrawal of support in patients who remain comatose. Achievement of awakening will likely increase the family's interest in continuing supportive care for this population. Consequently it is **critical** to evaluate rate of awakening and time to awakening in both an intervention and placebo group as delaying time to withdrawal may independently increase the rate of awakening.

Awakening is an appropriate short-term outcome as subjects who awaken survive and comprise all good outcomes by definition of CPC or mRS. Most tend to improve in functional status over the year after hospitalization. [19] Two-thirds of patients who awaken but do not survive to discharge die from multiple organ failure. This investigation proposes an early neurologic intervention that is unlikely to improve other organ failure. Thus, we have chosen a short-term neurologic outcome to maximize detection of a neurologic benefit to this intervention. If the rate of awakening is higher in the treatment arm, the face value of awakening would probably prompt clinicians to adopt the treatment. Furthermore, a larger trial powered to evaluate a treatment effect on long-term functional outcomes might be justified.

4.13 Daily Examinations

A study physician will complete a neurologic examination upon hospital arrival and again once the subject has rewarmed to a core temperature of $>36^{\circ}\text{C}$. [Table 4] The initial examination is used to determine the category of initial illness severity. [2] Daily examinations will not be performed until sedative medications have been discontinued for at least 40 minutes. [36] Our facility uses propofol for the majority of patients. In subjects receiving continuous infusion of midazolam, the midazolam will be discontinued for 60 minutes before examination. In the rare instance of neuromuscular blockade use, examinations will not be completed until the train of four monitor reads 4/4. Following rewarming, this examination will be completed daily. Prior literature has demonstrated that individual findings are less predictive for outcome in the modern era, thus, no one finding will result in cessation of support. [7, 37, 38]

[figure not shown]

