4.14 Prognostic Evaluation

Prior literature has demonstrated that individual physical exam or test findings are insufficient to preclude a good outcome. Therefore, no single finding will result in cessation of support. [7, 37, 38] A multimodal workup will be employed to predict neurologic outcome. This includes clinical examination, continuous EEG monitoring, computerized tomography, somatosensory evoked potentials, and magnetic resonance imaging. [Figure 4] The clinical examination is described in Table 4. Continuous EEG monitoring is described above.

Table 4. Clinical Examination of Comatose Post-Arrest Patients

Reflex	Method to Elicit	Potential Responses
Pupil Response	Light stimulus into each pupil for 5 seconds in a darkened room. A positive response will consist of any pupillary response to the light stimulus.	0- Absent 1- Present
Corneal Response	3 drops of sterile saline will be dropped onto the cornea from a distance of 5cm. If this does not elicit a corneal response, sterile gauze will gently be used to stimulate the cornea. Any blink response will be considered a positive response.	0- Absent 1- Present
Gag Response	A Yankauer catheter will be used to suction the posterior pharynx and tonsilar pillars. Gagging will be considered a positive response.	0- Absent 1- Present
Motor Response	Supraorbital pressure, pectoral pinch, and stimulation of the nailbeds with pressure exerted by forceps will be used to elicit a response. The best motor response will be recorded.	0- No response or myoclonus 1- Decorticate posturing 2- Decerebrate posturing or withdraw to pain 3- Localization 4- Following commands

Figure 4. Timeline and testing for neurologic prognostication. EEG- electroencephalogram; SSEP- somatosensory evoked potential; MRI- magnetic resonance imaging.

4.14.a Computerized tomography of the brain- Loss of grey-white differentiation (gray-white ratio of Hounsfield Units <1.2) on initial CT of the brain predicts survival and neurologic outcome following cardiac arrest. [39-41] Subjects with a grey-white ratio <1.2 will be excluded from the study.

4.14.b Somatosensory evoked potentials- Subjects without a motor response to painful stimuli (GCS Motor=1) at 72 hours following cardiac arrest will have SSEP's obtained as part of the standard protocol. A lack of N20 response bilaterally remains predictive for a poor neurologic outcome following cardiac arrest. [42]

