Kaplan-Meier curves will be generated for time-to-awakening for each treatment group and a log-rank statistic will be used to compare the cumulative probability of awakening across treatment groups. Those participants who are not awake by treatment day 7 will be considered censored observations. A Cox proportional hazards regression model will be used to compare time-to-awakening by treatment group controlling for baseline characteristics that are not balanced through random assignment and stratification variables. The assumptions of the Cox proportional hazards model will be evaluated (proportionality of the hazards model) and if violated, a split analysis will be conducted.

Aim 1, Hypothesis 2: A larger proportion of subjects will awaken during the first 7 days of treatment after administration of amantadine when compared to placebo.

A chi-square test will be used to compare the proportion of participants that are awake at day 7 between the two treatment groups. Logistic regression model will be used to compare the proportions by treatment group controlling for baseline characteristics that are not balanced through random assignment and stratification variables.

Aim 2: Determine if the number of serious adverse events differ between subjects randomized to amantadine and subjects randomized to placebo.

It is anticipated that given the severe critical state of those enrolled in the study, each study participant will have multiple serious adverse events. A t-test (or Wilcoxon test) will be used to compare the means number of serious adverse events that occurred during the 7 days after treatment initiation. A regression model will be used to compare the means after controlling for baseline characteristics that are not balanced through random assignment and stratification variables. The type of regression model will depend in the distribution of the number of serious adverse events and could be a linear regression model, negative binomial model, or Poisson model.

4.15.c Sample Size

The sample size calculations are based on the analysis approach for the primary hypothesis (Aim 1, Hypothesis 1) with a type I error rate of 0.05, a two-sided alternative hypothesis, and 80% power. Based on these assumptions, a sample of 120 (60 per treatment group) will be sufficient to detect a difference of awakening of 30% in the control group and 50% in the active treatment group.

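### The pre-dose motor score, recorded on the endpoint's own scale, is not pre-specified as a covariate in the Cox and logistic models

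*Combined protocol and SAP*

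**What the plan says.** **When severity is measured.** Section 4.13 describes an examination on hospital arrival and says: "The initial examination is used to determine the category of initial illness severity". Section 4.1 enrolls patients who are still comatose at hospital day 3.

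**The strata.** Section 4.15.a has four: PCAC IV, PCAC III, and PCAC II with and without malignant EEG. Section 4.11 places that EEG classification before randomization.

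**The later examinations.** Section 4.13 adds: "Following rewarming, this examination will be completed daily". In Table 4 (4.14) the motor item runs from 0 to 4 and "The best motor response will be recorded". Code 4 is following commands, which is how 4.1 defines awakening.

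**The analysis.** In 4.15.b, Hypothesis 1 is compared by log-rank test and then by Cox model. Hypothesis 2 is compared by chi-square test, after which a "Logistic regression model will be used to compare the proportions by treatment group". I read the covariate rule for both models as the stratification variables plus any baseline characteristic found unbalanced. No such characteristic is named. The log-rank and chi-square tests are described without strata or covariates.

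**The planning figures.** Section 4.15.c states that "a sample of 120 (60 per treatment group) will be sufficient". The effect assumed for that claim is given as a "difference of awakening of 30% in the control group and 50% in the active treatment group". The error rate and power behind it are those of steps shown below: two-sided 0.05 and 80%.

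**The concern.** By the time of randomization the PCAC category is days old, and everyone enrolled is meant to be still in coma. A patient who localizes at that point is one code below the endpoint; a patient with no motor response is at the bottom of the scale. If that difference predicts awakening within strata, a Cox or logistic model that omits it has less power than one that includes it. The estimate is also more exposed to chance differences in coma depth between arms. The score is already collected, so the information would be left out only because the plan does not name it.

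What is at stake is efficiency. Randomization keeps the tests valid with or without this covariate.

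**Working it through.** **1. The plan's own figure.** Inputs from 4.15.b and 4.15.c: 30% versus 50% awake by day 7, two-sided 0.05, 80% power, 60 per arm.

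- Hazard ratio implied under proportional hazards: ln(1 − 0.50)/ln(1 − 0.30) = 1.94, with logarithm 0.664.
- Events for 80% power (Schoenfeld): 4 × (1.960 + 0.8416)²/0.664² ≈ 71.1, so 72. At a mean event rate of 40%, N = 72/0.40 = 180.
- Expected events with 120 patients: 60 × 0.30 + 60 × 0.50 = 48. Power = Φ(√48/2 × 0.664 − 1.960) = Φ(0.34) ≈ 63%.
- Two proportions: n per arm = [1.960√(2 × 0.40 × 0.60) + 0.8416√(0.30 × 0.70 + 0.50 × 0.50)]²/0.20² = 93, so N = 186. Power at 60 per arm is 61%.

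The stated 120 does not reproduce. The unadjusted starting point is about 61% to 63%, not 80%.

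**2. What the documents do not give.** There is no motor-score distribution at enrollment and no association of the score with awakening. Both are assumed below. Marginal awakening is held at 30% and 50% throughout, with N = 120 and Wald tests at two-sided 0.05.

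**3. Set A.** Codes 0 to 3 at 25/15/40/20%, four strata; 1,000 Cox runs and 3,000 logistic runs per row.

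| Placebo awakening, lowest to highest code | Cox: strata, then plus score | Gain | Logistic: strata, then plus score | Gain |
|---|---|---|---|---|
| 17% to 45% | 66%, 71% | 5 | 65%, 66% | 1 |
| 10% to 56% | 65%, 74% | 9 | 62%, 69% | 7 |
| 5% to 66% | 68%, 83% | 15 | 63%, 75% | 12 |

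**4. Set B.** Four equal motor levels; four equal strata with hazard ratio 1.5 per level; daily assessment; censoring at day 7; no death or dropout; 3,000 trials per row. Power is for the Cox model.

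| Motor hazard ratio per level | Correlation with strata | Treatment only | Plus strata | Plus strata and score | Gain over strata |
|---|---|---|---|---|---|
| 1.0 | 0.3 | 62.0% | 66.2% | 65.9% | −0.3 |
| 1.35 | 0.3 | 63.4% | 69.4% | 71.4% | 2.0 |
| 1.65 | 0.3 | 63.5% | 69.5% | 76.5% | 6.9 |
| 2.23 | 0.3 | 65.4% | 71.4% | 85.2% | 13.8 |
| 3.0 | 0.3 | 66.8% | 73.4% | 94.3% | 20.9 |
| 1.65 | 0.6 | 63.4% | 72.6% | 77.5% | 4.9 |
| 2.23 | 0.6 | 65.7% | 77.8% | 88.4% | 10.6 |

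Gains are taken before rounding.

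**5. Set C.** Set A's score distribution, strata hazard ratio 1.5 per level independent of the score, 1,000 runs. Cox power went from 65% to 66% at a motor hazard ratio of 1.35 per level, and from 68% to 73% at 1.65.

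Monte Carlo standard error at 70% power is √(0.7 × 0.3/3000) = 0.8 point, or √(0.7 × 0.3/1000) = 1.4 points for 1,000 runs. The smallest gains cannot be told from zero.

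**6. Scale of the adjusted estimates.** The marginal odds ratio is (0.50/0.50)/(0.30/0.70) = 2.33. In Set A the conditional odds ratio for the same marginal effect was 2.56 to 3.16, and the conditional hazard ratio 2.05 to 2.37 against 1.94 in step 1. The adjusted odds ratio is therefore not a comparison of the proportions named in Hypothesis 2.

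**The case against.** The case for leaving the plan alone has several parts.

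- *The strata are not arrival severity alone.* A reader might infer that severity enters only through the arrival examination. The documents do not support that: PCAC II is split by malignant EEG seen before randomization, and 4.7 calls malignant EEG patterns that develop and persist prognostic independently of initial severity. What remains is that the split does not reach PCAC III or IV and does not measure motor function.
- *The score is not ignored.* A reader might infer that it is discarded. Table 2 uses absent motor response, together with an absent SSEP response, as an exclusion, and 4.15.b would admit the score if it were unbalanced. The accurate statement is that it is not pre-specified.
- *The gain may be small.* Section 4.13 describes individual findings as less predictive in the modern era, and the SSEP exclusion removes some patients at the bottom of the scale. This stands as a caution about size. The 4.13 remark, though, is made about ceasing support, and 4.14 includes the clinical examination in its prognostic workup.
- *The first-listed tests would not benefit.* The log-rank and chi-square tests carry no covariates. This stands in full: if those tests decide the hypotheses, the change adds no power to them.
- *No examination is timed to randomization*, and 4.13 withholds examinations until sedation or blockade has cleared. This stands. A score for every patient is likely but not guaranteed.
- *Omitting a covariate biases no test.* True, and it limits how serious the point is.

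**Conclusion.** The point holds as an inexpensive improvement in efficiency, not as an error in the plan. A baseline value on the endpoint's own scale is collected after the PCAC category is set, and its place in the models is left to chance imbalance.

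The size is unknown. Under assumed strengths, the Cox gain over the strata-only model is about 0 points if the score is not prognostic within strata, about 15 if it is strongly prognostic, and about 21 in the most extreme setting. It is smaller for the logistic model (1 to 12 points in Set A) and when the score correlates with PCAC. These figures rest on assumed score distributions and strengths; Set B also assumes proportional hazards and no death or dropout.

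Two stronger readings are not supported. One is that a loss of power has been shown; the documents contain nothing from which to measure it. The other is that adding the score would restore the stated 80%. Power passed 80% only in the strongly prognostic settings (5% to 66% in Set A; hazard ratio 2.23 or more per level in Set B), and only for the adjusted Cox model. The shortfall of 120 patients is a separate and larger matter that needs its own correction.

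**What to change.** In 4.15.b:

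1. Name the last Table 4 motor score before the first dose as a fixed covariate, whatever the observed balance, beside the randomization strata in the Hypothesis 1 Cox model and the Hypothesis 2 logistic model. Name the strata explicitly as well, since the present sentence can also be read as citing them only as a means of balance.
2. State the coding in advance: linear (1 degree of freedom) or categorical over codes 0 to 3 (3 degrees of freedom). Linear coding needs a reason, because code 2 puts decerebrate posturing and withdrawal together, above decorticate posturing.
3. Give a simple rule for a missing score that keeps the patient in the analysis and does not depend on arm. An example is the most recent earlier post-rewarming score, otherwise the stratum median.
4. Label the Cox result as a conditional hazard ratio. For Hypothesis 2, report from the logistic model the standardized difference in awakening proportion with its 95% CI.
5. State which analysis decides each hypothesis: the unadjusted test or the adjusted model.

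The cost is SAP wording and one to three degrees of freedom, with no new data collection. With treatment (1), strata (3) and score (1 or 3) the models have 5 or 7 terms. Against 48 expected awakenings that is 48/5 = 9.6 or 48/7 = 6.9 events per term, which favors fixing a short covariate list in advance.
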